The goal of this exploratory aim is to examine provider attitudes towards evidence-based treatment at baseline and perceptions of FBT at mid study (after experience with the intervention has been gained) as predictors of providers' future intention to use co-located FBT in their practices at the end of the study. We hypothesize that positive provider attitudes toward evidence-based treatment and perceptions of FBT will predict their intention to incorporate FBT into their practice settings. Appendix C provides details of the measures we will use in this aim. Because a provider's intention to incorporate FBT into their practice settings is measured on a broad scale ranging from 0% to 100%, we will treat the variable as a continuous variable and expect that random coefficient models will again be appropriate. Specifically, we plan to implement these models using PROC MIXED in SAS, with the provider nested within sites in those analyses. A strength of the planned analysis is that the anticipated 185 providers at the four sites will provide a rich opportunity to understand predictors of future intentions regarding the use of FBT. An uncertainty is that we currently have little data with which to predict the distribution of the 0% to 100% response variable. It is possible, therefore, that analyses in this exploratory aim will require data transformations, breaking the outcome measure into categories, or the use of

generalized estimating equations instead of mixed models. It should be noted that in contrast to earlier analyses, analyses of this aim do not involve group assignment and do not therefore reflect the overall IRGT trial design. Thus, only one covariance structure will be required.

E. Sensitivity Analyses

Sensitivity analyses to be performed in PLAN are as follows.

1. A modified intention-to-treat analysis of the primary outcome in which subjects who provided no follow-up data are excluded. These analyses will include imputed 24-month data using subjects who did provide data beyond baseline but who did not provide 24-month data.
2. To further facilitate an understanding of the impact of missing data on the primary result, the primary analysis will be repeated without imputation and using only subjects who provide both baseline and 24-month primary outcome data.

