"In home?" – Yes=1, No=0

"Child can immediately eat?" – Yes=1, No=0

"How much is there?" – A little=1, Some=2, A lot=3

28-45: Electronic Equipment

OVERALL TOTAL = The total number of electronics in the household: Sum the "total" row for all rooms (i.e., kitchen, living room, etc.), including the total for "in house (not always in 1 room)." If "total" for a given room is blank, code that room as 0.

46-58: Physical Activity

Each physical activity item can be given a total of 0, 1, or 2 points. Points are given – then summed to get the total points for that physical activity equipment item – based on availability and whether the child uses the item:

“Which of the following things are available and in usable condition in your home or yard/common area?”

Not available = 0, Available = 1

“If available, does your child commonly use this item?”

Yes = 1

No = 0

N/A = 0

Total score = sum of physical activity item points (items 41-53)

59-67: Cognitive Stimulation

A total of 0-28 points may be awarded based on the presence of cognitively-stimulating items in the child’s home. These questions are scored on different scales, as follows:

Item 59 (“How many books...”)

0 books = 0

1-10 books = 1

11-20 books = 2

21-30 books = 3

31-40 books = 4

41 or more books = 5

Items 60 – 64 (“How often does a parent...”)

Never = 0

Rarely = 1

Sometimes = 2

Often = 3

Very Often = 4

Items 65 – 67

Yes = 1

No = 0

Total score = sum of points awarded for items 59-67

Summary Score for Environmental Enrichment Questionnaire: Sum all subscales to create a global score of non-snack food reinforcers available to the child.

Attitudes toward Evidence-Based Treatment. (Exploratory Aim)

The following questions ask about your feelings about using new types of therapy, interventions, or treatments. Manualized therapy, treatment, or intervention refers to any intervention that has specific guidelines and/or components that are outlined in a manual and/or that are to be followed in a structured or predetermined way. **Indicate the extent to which you agree with each item using the scale shown below.**

	0 Not at all	1 To a slight extent	3 To a moderate extent	4 To a great extent	5 To a very great extent
1. I like to use new types of therapy/interventions to help my clients.					
2. I am willing to try new types of therapy/interventions, even if I have to follow a treatment manual.					
3. I know better than academic researchers how to care for my clients.					

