4. I am willing to use new and different types of therapy/interventions developed by researchers.					
5. Research-based treatments/interventions are not clinically useful.					
6. Clinical experience is more important than using manualized therapy/interventions.					
7. I would not use manualized therapy/interventions.					
8. I would try a new therapy/intervention, even if it were very different from what I am used to doing.					

For the following questions if you received training in a new therapy or intervention how likely would you be to adopt it if:

	0 Not at all	1 To a slight extent	3 To a moderate extent	4 To a great extent	5 To a very great extent
9. It was intuitively appealing?					
10. It made sense to you?					
11. It was required by your supervisor?					
12. It was required by the counseling center director?					
13. It was a state requirement?					
14. It was being used by colleagues who were happy with it?					
15. You felt you had enough training to use it correctly?					

Scoring guide for Attitudes Towards Evidence-Based Treatment

Scoring the Subscales

The score for each subscale is created by computing a total or mean score for the items that load on a given subscale. For example, Items 11, 12, and 13 constitute subscale 1.

Subscales

Requirements

Items: 11, 12, 13

Appeal

Items: 9, 10, 14, 15

Openness

Items: 1, 2, 4, 7

Divergence

Items: 3, 5, 6, 7

Computing the Total Scale Score

For the total score, all items from the Divergence subscale (Sub-scale 4) must be reverse scored before being used in computing the EBPAS total score.

Attributes of FBT. (Exploratory Aim)

Given your knowledge and understanding of FBT, please respond to the following questions.

1. Using FBT in the clinic was more effective than the clinic's existing treatment method.

1 2 3 4 5

Strongly Agree

Strongly Disagree

2. The content of FBT is compatible with my personal beliefs and values.

1 2 3 4 5

Strongly Agree

Strongly Disagree

3. FBT is useful.

1 2 3 4 5

Strongly Agree

Strongly Disagree

4. FBT is credible.

1 2 3 4 5

Strongly Agree

Strongly Disagree

5. FBT is easy to administer in the practice setting.

1 2 3 4 5

Strongly Agree

Strongly Disagree

6. The content of FBT is clear.

1 2 3 4 5

Strongly Agree

Strongly Disagree

7. The content of FBT is relevant to my work as a medical treatment provider.

1 2 3 4 5

Strongly Agree

Strongly Disagree

8. FBT can be experimented without requiring an extensive involvement.

1 2 3 4 5

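### The Appendix C key for the provider attitude measure in Exploratory Aim 1 puts negatively worded item 7 in two subscales and item 8 in none, so Openness is mis-scored if computed as printed (minor)

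*Combined protocol and SAP*

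**What the plan says.** Section III, D. Analysis of Exploratory Aim 1, sets out to "examine provider attitudes towards evidence-based treatment at baseline and perceptions of FBT at mid study" as predictors of intention to use co-located FBT at the end of the study. About 185 providers are anticipated. The section gives no scoring rule of its own and refers the reader on: "Appendix C provides details of the measures we will use in this aim". It does not say whether subscale scores or a total score enter the model.

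The scoring guide for the attitude measure in Appendix C has four parts that matter here.

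- **Subscale rule.** "The score for each subscale is created by computing a total or mean score for the items that load on a given subscale". No reversal is mentioned at this step.
- **Key.** Requirements is items 11, 12, 13. Appeal is "Items: 9, 10, 14, 15". Openness is items 1, 2, 4, 7. Divergence is items 3, 5, 6, 7.
- **Total.** All Divergence items are to be reverse scored before the total is computed. No reversal formula is given.
- **Response codes.** Both provider response tables print 0, 1, 3, 4, 5 against five labels, the middle one being "3 To a moderate extent".

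Item 7 reads "I would not use manualized therapy/interventions". Item 8 reads "I would try a new therapy/intervention, even if it were very different from what I am used to doing".

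**The concern.** The four lists contain 15 entries for 15 items, yet one item appears twice and one not at all. The duplicated item is unfavourable and sits in Openness beside three favourable items. The omitted item is favourable and worded like those three. The guide is also inconsistent with itself: its total-score rule treats item 7 as unfavourable, while its Openness list adds the same item with no change of sign.

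An analyst who follows the key would therefore build an Openness score in which one of four items pulls against the rest. If that score is a predictor in the model, its relation to intention to adopt FBT is likely to look weaker than it is. The gap in the response codes is a second, smaller flaw in the same guide.

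**Working it through.** **1. Count the key.** Requirements {11, 12, 13}, Appeal {9, 10, 14, 15}, Openness {1, 2, 4, 7} and Divergence {3, 5, 6, 7} give 3 + 4 + 4 + 4 = 15 entries. Item 7 is used twice and item 8 never. With 8 in place of 7 in Openness, each of items 1 to 15 is used exactly once.

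**2. Score extreme providers with the printed codes.** The most favourable provider answers 5 to favourable items and 0 to unfavourable ones (3, 5, 6, 7). The least favourable does the opposite.

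| Openness mean | Most favourable | Least favourable | Span |
|---|---|---|---|
| As printed (1, 2, 4, 7) | (5+5+5+0)/4 = 3.75 | (0+0+0+5)/4 = 1.25 | 2.5 |
| With item 8 (1, 2, 4, 8) | 5 | 0 | 5 |

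The span is halved. With consecutive codes 0-4 the figures are 3 and 1 against 4 and 0, again half, so this does not depend on the code gap.

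**3. Follow the slip into the total**, with reversal taken as 5 - x (an assumption).

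- Mean of all 15 items, Divergence items reversed: extremes 5 and 0. Item 7 enters once, reversed, and item 8 enters once, so the slip does no harm.
- Mean of the four printed subscales, Divergence reversed: (5 + 5 + 3.75 + 5)/4 = 4.69 and (0 + 0 + 1.25 + 0)/4 = 0.31. Item 8 is lost and item 7 enters with both signs.

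**4. Gauge the attenuation.** The documents give no inter-item correlations, so these are assumed: r = 0.3 to 0.5 among items 1, 2, 4, 8, and q = -0.2 to -0.4 between each of them and item 7, with equal variances.

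- Correlation of printed Openness with the 1, 2, 4, 8 score = (3 + 9r + 4q) / √[(4 + 12r)(4 + 6r + 6q)]. At r = 0.3, q = -0.4: 4.1/√(7.6 × 3.4) = 0.81. At r = 0.5, q = -0.2: 6.7/√(10 × 5.8) = 0.88.
- Cronbach's alpha = (4/3)(1 - 4/V), where V is the variance of the sum. For items 1, 2, 4, 8, V = 4 + 12r gives 0.63 to 0.80. As printed, V = 4 + 6r + 6q gives -0.24 to 0.41.
- If, further, a single factor drives all five items and their link to intention, the share of the correlation kept is (3r + q)√(4 + 12r) / [4r√(4 + 6r + 6q)]. This is 0.62 at r = 0.3, q = -0.4 and 0.85 at r = 0.5, q = -0.2.

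**5. The code gap.** The steps are 1, 2, 1, 1. Under 5 - x, the codes 0, 1, 3, 4, 5 become 5, 4, 2, 1, 0, and 2 is not a printed code. A middle answer then counts 3 on ordinary items and 2 on the four reversed ones, so a provider who gives it throughout has a 15-item mean of (11 × 3 + 4 × 2)/15 = 2.73 rather than 3. The effect is small: if the five options are used equally often (assumed), the printed codes correlate 13/√(17.2 × 10) = 0.99 with 0-4. Under 4 - x on consecutive codes the middle answer is 2 both ways.

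**The case against.** A fair defence makes four points, and most of them narrow the matter rather than remove it.

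- **Scope.** A reader might infer that provider attitude scores in general are wrong, or that the predictor in the hypothesis is itself mis-scored. The documents do not support that. The hypothesis speaks of positive attitudes as a whole and names no subscale. Three of the four item lists are sound, and a 15-item total is untouched by the slip. This stands. But the plan does not say which score it will use, so the faulty Openness score remains a permitted choice.
- **Direction of harm.** A reader might also infer that the key could produce a null or reversed association. Correlations of 0.81 to 0.88 with the corrected score point to attenuation. If items 1, 2 and 4 each have covariance c with intention, the sign turns only when item 7's negative covariance exceeds 3c in size, and nothing in the documents suggests that. This stands.
- **Stored data.** Appendix C shows a form and a scoring note, not the REDCap codes or the SAS scoring program, so the slip may exist only on paper. This stands as a qualifier: the finding is about scores computed as printed.
- **Weight of the code gap.** The codes keep the order of the answers, and 5 - x is not stated in the guide. The coach form codes the same five labels 1 to 5, but no provider-coach comparison is planned in this aim, so that difference has no analytic consequence here. This stands; the gap is worth tidying and no more.

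**Conclusion.** The key is wrong as printed for one subscale. Openness computed from it has half its proper span between the most and least favourable provider, which follows from the key and codes alone. That any association with intention is attenuated is probable rather than shown. The 0.62 to 0.85 retained share rests on assumed correlations and a single-factor model. A total is affected by the key only if it is assembled from the printed subscales. The uneven codes add a small distortion, and the uneven reversal appears only if reversal is 5 - x.

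Severity is minor. The aim is exploratory, the primary and secondary analyses do not use this measure, and nothing is lost if item-level responses are kept.

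**What to change.** - In the Appendix C scoring guide, set Openness to items 1, 2, 4, 8 and keep Divergence as items 3, 5, 6, 7, so that each item is used once. This follows from the wording of the items in the appendix.
- Confirm the codes stored in REDCap. Recode to consecutive values 0-4 before scoring, and state the reversal as 4 - x.
- In section D, Analysis of Exploratory Aim 1, state whether the total or the subscales enter the model and, if the total, that it is computed from the 15 items.
- Compute all scores from item-level responses with the corrected key.

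The cost is a short correction to the key, a sentence or two in section D and a run of the scoring program. No new data or change of design is needed.

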Strongly Agree

Strongly Disagree

9. FBT can be adapted or modified to suit the needs of the interventionist.

1 2 3 4 5

Strongly Agree

Strongly Disagree

10. The benefits of using FBT with my patients are obvious/visible.

1

2

3

4

5

Strongly Agree

Strongly Disagree

11. The evidence regarding the impact of FBT is available.

1

2

3

4

□

Strongly Agree

Strongly Disagree

Scoring for Attributes of FBT:

The scale is composed of five subscales: Relative advantage (1), compatibility (2-4), complexity (5-7), trialability (e.g., the potential to experiment with an innovation before implementing; 8-9), and observability (10-11). If the subscale has more than one item, the subscale score is created by computing a total or mean score for the items that load on a given subscale.

Intended Adoption. (Exploratory Aim)

How likely is it that you will use this model of having a co-located interventionist to treat children who are overweight/obese as a result of your experiences with an FBT interventionist within your practice?

0% _____ 100%

Scoring: Physicians will place an X on the electronic line to signal their percentage likelihood.

Family Demographics. (Descriptor)

Please put an X in the appropriate box for your mother's, your father's, your spouse / partner's, and your level of school completed and occupation. If the exact occupation is not listed, please put an X by the category that most closely matches the individual's occupation, and if a parent is retired, please indicate their most recent occupation. If you grew up in a single parent home, mark only your one parent, and mark "N/A" for the other parent. If you are neither married nor partnered, mark "N/A" for Spouse/Partner.

A. Level of School completed	Mother	Father	Spouse/Partner	You
(N/A)				
Less than 7 th grade				
Junior high / Middle school (up to 9 th grade)				
Partial high school (10 th or 11 th grade)				
High school graduate				
Partial college (at least one year)				
College education				
Graduate degree				

B. Occupation	Mother	Father	Spouse/Partner	You
(N/A or stay-at-home parent)				
Day laborer, janitor, house cleaner, farm worker, food counter sales, food preparation worker, busboy.				
Garbage collector, short-order cook, cab driver, shoe sales, assembly line workers, masons, baggage porter.				
Painter, skilled construction trade, sales clerk, truck driver, cook, sales counter, or general office clerk.				

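### The Exploratory Aim 1 model groups providers only by site and leaves out practice, so standard errors may be too small, mainly for month-12 perceptions of FBT

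*Combined protocol and SAP*

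**What the plan says.** The SAP section Analysis of Exploratory Aim 1 sets out to "examine provider attitudes towards evidence-based treatment at baseline". Its second predictor, from later in the trial, is "perceptions of FBT at mid study (after experience with the intervention has been gained". What these two measures are meant to predict is the "future intention to use co-located FBT in their practices at the end of the study". That outcome is a 0% to 100% rating treated as continuous. On software the section states: "we plan to implement these models using PROC MIXED in SAS". The only nesting it specifies is "with the provider nested within sites in those analyses". The section counts as a strength that "the anticipated 185 providers at the four sites will provide a rich opportunity". Because treatment arm does not enter this aim, it concludes: "Thus, only one covariance structure will be required". If the outcome's distribution is awkward, it allows transformation, categorisation or generalized estimating equations (GEE); no cluster unit is named for the GEE.

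Table 4 (Measurement Timeline) marks attitudes at baseline, Attributes of FBT at month 12 and Intended Adoption at month 24, once each. In Appendix C the Intended Adoption item asks how likely the provider is to use the co-located model "as a result of your experiences with an FBT interventionist within your practice". Two Attributes of FBT items likewise ask the provider to judge FBT in the clinic or practice setting.

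**The concern.** A random effect for provider absorbs correlation only if a provider contributes more than one outcome. Here each contributes one, so the term is indistinguishable from residual error. The only working grouping left is site, with four levels.

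The level at which answers are most likely to be alike is the practice. Colleagues there see FBT delivered in the same space and workflow, largely by the same coach, and the outcome item refers to that setting. If intention and a predictor both run high in some practices and low in others, a model that treats providers within a site as independent counts more information than it has. The predictor's standard error is then too small and its p-value too low.

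At stake is how firmly the trial can say that perceptions of FBT predict intended adoption. The efficacy results are not involved.

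**Working it through.** The plan gives no power, effect size, ICC or standard error for this aim, so there is no figure to reproduce.

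**Inputs from the documents.** 185 providers and four sites (Analysis of Exploratory Aim 1); one outcome per provider at month 24 (Table 4); two-sided 0.05 level (Statistical Analysis Plan); three coaches per site, so 12, plus backup and floating coaches at some sites (Primary Analysis; Masking of Assessment Staff).

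**Assumptions.** The number of practices is not stated; 15 to 40 is assumed, with 12 and 46 as outer cases in the simulation. No practice-level ICC is given; values from 0 to 0.2 are tried for the predictor (ICC_x) and the outcome (ICC_y).

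**Step 1: can the provider term be estimated?** Take a site variance of 0.1 and a further variance of 1.0 split between provider and residual. With four sites, five providers each and one outcome per provider, splits of 0.2/0.8, 0.5/0.5 and 0.8/0.2 all give variance 1.1, within-site covariance 0.1 and log-determinant 1.6219. The likelihood cannot tell them apart.

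**Step 2: effect on the slope SE when practice is ignored.** With m providers per practice:

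- true SE / model SE = sqrt(1 + (m − 1) × ICC_x × ICC_y)
- actual level = 2 × P(Z > 1.96 / ratio)

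For 40 practices m = 185/40 = 4.625; for 15 practices m = 185/15 = 12.33.

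| ICC_x / ICC_y | 40 practices | 15 practices |
|---|---|---|
| 0 / 0.2 | ratio 1; level 5.0% | ratio 1; level 5.0% |
| 0.05 / 0.05 | sqrt(1.009) = 1.005; 5.1% | sqrt(1.028) = 1.014; 5.3% |
| 0.1 / 0.1 | sqrt(1.036) = 1.018; 5.4% | sqrt(1.113) = 1.055; 6.3% |
| 0.2 / 0.2 | sqrt(1.145) = 1.070; 6.7% | sqrt(1.453) = 1.206; 10.4% |

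The ratio is how far the true SE exceeds the model SE. At 1.206 the true SE is 21% larger; put the other way, the model SE is 17% too small (1 − 1/1.206).

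**Step 3: simulation with a true slope of zero.** 185 providers were spread over four sites.

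- Site-only model (4,000 runs per setting), ICCs 0.2/0.2: type I error 0.063 with 46 practices, 0.085 with 20 and 0.102 with 12.
- Site-only model, ICC_x = 0: 0.042 to 0.053, so no inflation.
- Model with a practice random intercept (1,500 runs per setting), with 12, 20 or 46 practices and ICCs from 0/0.1 to 0.3/0.3: 0.043 to 0.059, with mean SE over empirical SD between 0.97 and 1.03.

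**The case against.** A reader might infer that the standard errors are too small as a matter of fact, for attitudes and perceptions alike. The documents do not support that. Understatement needs positive within-practice correlation in both predictor and outcome, and no ICC or practice count is given. Baseline attitudes are measured before any exposure to a coach in the practice, so shared experience of FBT cannot have made them alike. This objection stands and limits the point to a possibility, strongest for month-12 perceptions.

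Shared exposure is also imperfect. Backup and floating coaches work across caseloads and practices (Masking of Assessment Staff), sessions may be held away from the practice (Randomization), and they moved to remote platforms during the pandemic (Remote Assessments). This weakens the mechanism without removing it, since the questionnaire items still refer to the provider's own clinic or practice. It also means coach could be the relevant cluster: 185/12 is about 15.4 providers per coach, and a practice intercept would not absorb correlation running across one coach's practices.

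The nesting phrase may only describe a hierarchy, with providers as the observations inside sites and no separate provider effect intended. That is a fair reading, and on it nothing is unidentifiable. The model still stops at four sites.

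Finally, the aim is exploratory and its model is presented as provisional. The alternatives listed, however, address the outcome's distribution. The SAP's general undertaking to check that its analyses are appropriate (Assessing the Appropriateness of Analytic Strategies) does not mention clustering. The absence of treatment arm justifies one covariance structure; it does not justify omitting practice.

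**Conclusion.** The point holds as a low-cost improvement. As written, the model amounts to site plus residual, and practice, the setting that the outcome item names, is missing. That part needs no assumption beyond the single month-24 measurement.

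The consequence is conditional. For month-12 perceptions, with 15 to 40 practices, the model SE could fall short of the true one by a trivial amount (ICCs of 0.05 or less) or by enough to put a nominal 5% test at about 10% (ICCs of 0.2/0.2 with 15 practices). For baseline attitudes the case is weaker, and if a predictor does not cluster by practice there is no inflation. These figures rest on assumed practice counts and ICCs. Nothing here bears on the primary or secondary aims.

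**What to change.** In Analysis of Exploratory Aim 1, replace the provider-within-site nesting with a random intercept for practice within site, keep site in the model, and specify no separate provider random effect. State that practice is the cluster if GEE is used; clustering on site would leave only four clusters. Add a sensitivity analysis with coach as the cluster, because one coach may cover several practices. Whether site is fixed or random, and which degrees-of-freedom method is used, are secondary choices.

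The cost is a few sentences of SAP text and slightly wider intervals if practices differ; if the practice ICCs are near zero, almost nothing is lost. Each provider's practice must be in the analysis dataset. That is a reasonable inference, since providers take part through participating practices, but the documents do not state it and it should be confirmed.
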